2. INTRODUCTION

This SAP provides the detailed methodology for summary and statistical analyses of the data collected in study B9991009. This document may modify the plans outlined in the protocol; however, any major modifications of the primary endpoint definition or its analysis will also be reflected in a protocol amendment.

CCI [REDACTED]

Statistical analyses will be performed using cleaned eCRF data as well as non-CRF data (ie, PK concentration, ADA, nAb, CCI [REDACTED]), and tumor assessment results by the Blinded Independent Central Review (BICR)).

The primary analysis will include all data up to a cut-off date which is determined by the number of events for Progression-Free Survival (PFS) by Blinded Independent Central Review (BICR) and for Overall Survival (OS) and minimum follow-up of 12 months after the last patient is randomized. The cut-off date is determined once a data extract (before database lock) is available which indicates that the required number of events for PFS by BICR and for OS and minimum follow-up of 12 months have occurred.

Due to data cleaning activities, the final number of events might deviate from the planned number. The data cut-off date will not be adjusted retrospectively in this case.

2.1. Study Objectives

Primary Objectives

- To demonstrate that avelumab given alone or in combination with Pegylated liposomal doxorubicin (PLD) is superior to PLD alone in prolonging OS in patients with platinum-resistant/platinum-refractory ovarian cancer.
- To demonstrate that avelumab given alone or in combination with PLD is superior to PLD alone in prolonging PFS in patients with platinum-resistant/platinum-refractory ovarian cancer.

Secondary Objectives

- To evaluate anti-tumor activity of avelumab given alone or in combination with PLD versus PLD alone in ovarian cancer patients.

- To evaluate the overall safety profile of avelumab alone or in combination with PLD versus PLD alone in ovarian cancer patients.
- To characterize the Pharmacokinetics (PK) of doxorubicin (PLD samples) and avelumab when administered in combination, and to assess the effect of avelumab on the PK of doxorubicin (PLD samples) and the effect of PLD on PK of avelumab.
- To assess the immunogenicity of avelumab.
- To evaluate candidate predictive biomarkers of sensitivity or resistance to avelumab alone or PLD in combination with avelumab in pre-treatment tumor tissue, that may aid in the identification of patient subpopulations most likely to benefit from treatment.
- To compare the effect of avelumab alone or in combination with PLD versus PLD alone on patient-reported outcomes (PRO) in patients with ovarian cancer.

Exploratory Objectives

- CCI [REDACTED]
- [REDACTED]

2.2. Study Design

This is a Phase 3, multicenter, randomized, open-label, parallel 3-arm study in which approximately 550 patients will be randomized in a 1:1:1 ratio to receive avelumab alone, avelumab in combination with PLD, or PLD alone, as follows:

- Arm A: avelumab alone;
- Arm B: avelumab plus PLD;
- Arm C: PLD alone.

Patients will be stratified by platinum-refractory or platinum-resistant status, number of prior regimens (1 vs 2 or 3), and bulky disease (defined as presence of a tumor ≥ 5 cm) vs not. Cross-over will not be permitted.

3. ENDPOINTS AND BASELINE VARIABLES: DEFINITIONS AND CONVENTIONS

3.1. Primary Endpoints

- Overall Survival (OS).

OS is defined as the time from the date of randomization to the date of death due to any cause.

- Progression Free Survival as determined by BICR according to RECIST version 1.1.

PFS is defined as the time from the date of randomization to the date of the first documentation of progressive disease (PD) or death due to any cause, whichever occurs first.

3.2. Secondary Endpoints

3.2.1. Safety endpoints

- Adverse Events (as graded by NCI CTCAE v.4.03);

AEs will be graded by the investigator according to the Common Terminology Criteria for Adverse Events (CTCAE) version 4.03 and coded using the Medical Dictionary for Regulatory Activities (MedDRA)

- Laboratory abnormalities (as graded by NCI CTCAE v.4.03);
- Vital signs (blood pressure, pulse rate);
- Electrocardiograms (ECGs), ECHO or MUGA scans.

3.2.2. Efficacy endpoints

- PFS as determined by Investigator according to RECIST version 1.1.
- Objective Response (OR), Duration of Response (DR), and Disease Control (DC) as determined by Blinded Independent Central Review (BICR) and Investigator [as assessed by RECIST version 1.1].

OR is defined as complete response (CR) or partial response (PR) according to RECIST v1.1 from the date of randomization until the date of the first documentation of PD. Both CR and PR must be confirmed by repeat assessments performed no less than 4 weeks after the criteria for response are first met.

DR is defined, for patients with an objective response, as the time from first documentation of objective response (CR or PR) to the date of first documentation of PD or death due to any cause.

DC is defined as CR, PR, non-CR/non-PD, or SD. Both CR and PR must be confirmed by repeat assessments performed no less than 4 weeks after the criteria for response are first met. Criteria for SD and non-CR/non-PD must have been met at least 6 weeks after the date of randomization.

3.2.3. Patient reported outcomes

- EORTC QLQ-C30, EORTC QLQ-OV28, and EQ-5D-5L.

Patient-reported outcomes of HRQoL and ovarian cancer specific disease/treatment-related symptoms will be evaluated using the European Organization for Research and Treatment of Cancer Quality of Life Questionnaire – Core 30 (EORTC QLQ-C30) and its corresponding module for ovarian cancer, the Quality of Life Questionnaire – Ovarian Cancer 28 (QLQ-OV28). The EuroQoL 5 Dimensions 5 Levels (EQ-5D-5L) questionnaire will also be collected to assess general health status.

The EORTC QLQ-C30 consists of 30 questions which assess five functional domains (physical, role, cognitive, emotional, and social), global health status/quality of life, disease/treatment related symptoms (fatigue, pain, nausea/vomiting dyspnea, appetite loss, sleep disturbance, constipation, and diarrhoea), and the perceived financial impact of disease (Aaronson et al. 1993, Aaronson et al. 1996, Osoba et al. 1997).

The EORTC QLQ-OV28 is the ovarian cancer specific module of the EORTC quality of life questionnaire. The EORTC QLQ-OV28 is a 28 item instrument with seven (7) functional domain subscales. The 7 subscales include:

- (i) an abdominal/GI symptom subscale (7 items);
- (ii) a peripheral neuropathy subscale (3 items);
- (iii) a chemotherapy side effects subscale (7 items);
- (iv) a hormonal/menopausal symptoms subscale (2 items);
- (v) a body image subscale (2 items);
- (vi) an attitude to disease and treatment subscale (3 items); and
- (vii) a sexual function subscale (4 items).

Higher scores are reflective of a greater presence of symptoms (Cull et al. 2001, Greimal et al. 2003).

The EQ-5D-5L questionnaire consists of the EQ-5D-5L descriptive system and a visual analogue scale (the EQ VAS). The EQ-5D-5L descriptive system measures a patient's health state on 5 dimensions which include: mobility, self-care, usual activities, pain/discomfort, and anxiety/depression. The respondent's self-rated health is assessed on a scale from 0 (worst imaginable health state) to 100 (best imaginable health state) by the EQ-VAS (The EuroQol Group, 2015).

3.2.4. Pharmacokinetic endpoints

- Pharmacokinetic parameters C_{trough} for avelumab: C_{max}, volume of distribution (V_d), clearance (CL), area under the concentration-time curve (AUC) for doxorubicin (PLD samples).

C_{max} and C_{trough} are calculated after single dose and at steady state. Other parameters will be calculated including, but not limited to T_{max} , AUC_{24} , AUC_{last} , T_{last} , $AUC_{sd,\tau}$, $AUC_{ss,\tau}$, $t_{1/2}$, CL , and Vd_z , $C_{ss,av}$ as data permit). Dose normalized parameters (eg, $CDN-C_{max}$, $DN-AUC$) will be reported as appropriate.

Table 2. PK Parameters to be Determined for Avelumab and Doxorubicin

Parameter	Definition	Method of Determination
AUC_{24}	Area under the plasma concentration-time profile from time zero to 24 hours	Linear/Log trapezoidal method
AUC_{last}	Area under the plasma concentration-time profile from time zero to the time of the last quantifiable concentration (C_{last})	Linear/Log trapezoidal method
$AUC_{sd,\tau}$ $AUC_{ss,\tau}$	Area under the plasma concentration-time profile after single dose from time zero to the next dose (after single dose and at steady state)	Linear/Log trapezoidal method
C_{max}	Maximum observed plasma concentration	Observed directly from data
T_{max}	Time for C_{max}	Observed directly from data as time of first occurrence
$t_{1/2}^a$	Terminal half-life	$\text{Log}_e(2)/k_{el}$, where k_{el} is the terminal phase rate constant calculated by a linear regression of the log-linear concentration-time curve. Only those data points judged to describe the terminal log-linear decline were used in the regression.
C_{trough}	Predose concentration during multiple dosing	Observed directly from data
CL	Clearance	Dose / $AUC\tau$ for steady state
Vd	Volume of distribution	Dose / ($AUC\tau \cdot k_{el}$) for steady state
$AUC_{24} (dn)$	Dose normalized AUC_{24}	AUC_{24} / Dose
$AUC_{last} (dn)$	Dose normalized AUC_{last}	AUC_{last} / Dose
$AUC_{inf} (dn)^a$	Dose normalized AUC_{inf}	AUC_{inf} / Dose
$C_{max} (dn)$	Dose normalized C_{max}	C_{max} / Dose

^a If data permit

3.2.5. Immunogenicity endpoints

- Anti-Drug antibodies and neutralizing antibodies against avelumab.

Anti-Drug Antibody (ADA) / Neutralizing antibodies (nAb) titers for avelumab.

3.2.6. Biomarker endpoints

- Candidate predictive biomarkers in tumor tissue including, but not limited to, PD-L1 expression and tumor infiltrating CD8+ T lymphocytes as assessed by immunohistochemistry (IHC).

Table 3. Biomarker Definition and Determination

Parameter	Definition	Method of Determination
PD-L1 expression	The number of PD-L1 positive cells and/or qualitative assessment of PD-L1 staining on tumor and inflammatory cells in regions of interest that are defined by tumor cell morphology and the presence or absence of CD8+ cells	Pathologist, assisted by image analysis
Tumor infiltrating CD8+ lymphocytes	The number of CD8+ cells per unit area and the percent of counted cells that are scored as CD8+	Pathologist, assisted by image analysis

3.3. Exploratory Endpoints

CCI

- CA-125 levels.

3.4. Baseline Variables

3.4.1. Study drug, study treatment and baseline definitions

In this study, ‘study drug’ refers to avelumab or PLD and ‘study treatment’ (or ‘treatment arm’) refers to one of the following:

- Arm A = avelumab alone;
- Arm B = avelumab plus PLD;
- Arm C = PLD alone.

Start and end dates of study treatment:

For Arm A and Arm C:

The date/time of first dose of study treatment is the earliest date/time of non-zero dosing of the study drug.

The date/time of last dose of study treatment is the latest date/time of non-zero dosing of the study drug.

For Arm B:

The date/time of first dose of study treatment in the combination arm is the earliest date/time of the first non-zero dose date/time for each of the study drugs.

The date/time of last dose of study treatment in the combination arm is the latest date/time of the last non-zero dose date/time for each of the study drugs.

Definition of baseline:

Definition of baseline for efficacy and PRO analyses

The last measurement prior to randomization will serve as the baseline measurement for efficacy and PRO analyses. If such a value is missing (since per protocol the first PRO assessment is planned to occur prior to dosing on Cycle 1 Day 1), the last measurement prior to the first dose of study treatment will be used as the baseline measurement except for analyses of tumor assessments data where the baseline assessment would be considered as missing.

Definition of baseline for immunogenicity analyses

The last available assessment prior to the start of treatment with avelumab is defined as ‘baseline’ result or ‘baseline’ assessment. If an assessment is planned to be performed prior to the first dose of avelumab in the protocol and the assessment is performed on the same day as the first dose of avelumab, it will be assumed that it was performed prior to avelumab administration, if assessment time point is not collected or is missing.

Definition of baseline for safety analyses

The last available assessment prior to the start of study treatment is defined as ‘baseline’ value or ‘baseline’ assessment for safety analyses. If an assessment is planned to be performed prior to the first dose of study treatment in the protocol and the assessment is performed on the same day as the first dose of study treatment, it will be assumed that it was performed prior to study treatment administration, if assessment time point is not collected or is missing. If assessment time points are collected, the observed time point will be used to determine pre-dose on study day 1 for baseline calculation. Unscheduled assessments will be used in the determination of baseline. However, if time is missing, an unscheduled assessment on study day 1 will be considered to have been obtained after study treatment administration.

Patients who start treatment and discontinue from the study on the same day may have two different sets of data collected on study day 1 (one during study and one in the End of Treatment (EOT) visit). Data reported at the EOT visit are not eligible for baseline selection.

If a scheduled pre-dose measurement actually occurred post-dose, then the corresponding measurement will be treated and analyzed similar to an unscheduled post-dose measurement.

Baseline for RR and QT/QTc interval assessments will be derived from the visit where both RR and QT are not missing. Triplicate ECGs are collected in the study and the baseline for each ECG measurement is the average of the pre-dose replicate measurements on the baseline day. Unscheduled assessments will not be included in the calculation of the average. QTcB and QTcF will be derived based on RR and QT. The average of the replicate measurements will be determined after the derivation of the individual parameter at each time point.

Definition of baseline for biomarker analyses

The last measurement prior to the start of study treatment will serve as the baseline measurement for biomarker analyses. For biomarkers that are planned to be measured on Cycle 1 Day 1 (eg, soluble proteins), it will be assumed that the measurement was performed prior to study treatment administration, if the assessment time point is not collected or is missing.

3.4.2. Baseline characteristics

Randomization is stratified by the following, as recorded in the Interactive Response Technology (IRT):

090177e19142bcd4\Approved\Approved On: 09-Jul-2019 05:44 (GMT)

- Platinum-refractory or platinum-resistant status
- Number of prior regimens (1 vs 2 or 3)
- Bulky disease (defined as presence of a tumor ≥ 5 cm) vs not

The primary analyses of OS and PFS will be stratified by these randomization stratification factors.

Other baseline characteristics (including demographics, physical measurements, disease history and prior anti-cancer therapies) are described in Section 6.5.1. These baseline characteristics are not planned to be included as stratification variables or covariates in statistical models unless otherwise specified in Section 6.

3.5. Safety Endpoints

3.5.1. Adverse events

Treatment-Emergent Adverse Events

Treatment-emergent adverse events (TEAEs) are those events with onset dates occurring during the on-treatment period for the first time, or if the worsening of an event is during the on-treatment period.

On-treatment period is defined as the time from the first dose of study treatment through minimum (30 days + last dose of study treatment, start day of new anti-cancer drug therapy – 1 day). The start day of new anti-cancer drug therapy after the first dose of study treatment is derived as outlined in Section 5.2.5.

Adverse Events of Special Interest (AESIs)

AESIs are immune-related adverse events (irAE) and infusion-related reactions (IRRs). The criteria for classification of an AE as an irAE or IRR are described in Appendices 1 and 2, respectively.

3-Tier Adverse Events

It should be recognized that most studies are not designed to reliably demonstrate a causal relationship between the use of a pharmaceutical product and an adverse event or a group of adverse events. Except for select events in unique situations, studies do not employ formal adjudication procedures for the purpose of event classification. As such, safety analyses are generally considered as an exploratory analysis and its purpose is to generate hypotheses for further investigation. The 3-tier approach facilitates these exploratory analyses.

Adverse events and clusters of adverse events, of any causality and treatment-related, will also be summarized following a 3-tier approach. Under this approach, AEs are classified into 1 of 3 tiers.

Tier-1 events: These are pre-specified events or clusters of events of clinical importance and will be described in the Safety Review Plan.

Tier-2 events: These are events that are not Tier-1 but are “common”. A MedDRA PT is defined as a Tier-2 event if it is reported by

- a) at least 10% of patients with any grade in any treatment arm, or
- b) at least 5% of patients with Grade 3, 4 or 5 in any treatment arm.

Tier-3 events: All other AEs that are classified neither as Tier-1 nor Tier-2.

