7.1.2. Adverse Events

7.1.2.1. Adverse Events of Special Interest for Avelumab

- Any AE that is suspected to be a potential irAE is considered an AE of special interest (AESI). Specific guidance for the management of immune-related AEs is provided in [Section 5.2.7.2.3](#), [Appendix 9](#) Avelumab Management of Immune-related Adverse Events. AESIs are reported according to the general AE reporting rules specified in [Section 8.2](#).

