Appendix 9. Management of Immune-related Adverse Events

Gastrointestinal irAEs		
Severity of Diarrhea/Colitis (NCI-CTCAE v4)	Initial Management	Follow-up Management
Grade 1 Diarrhea: <4 stools/day over Baseline Colitis: asymptomatic	Continue avelumab therapy Symptomatic treatment (eg, loperamide)	Close monitoring for worsening symptoms Educate subject to report worsening immediately If worsens: Treat as Grade 2, 3 or 4
Grade 2 Diarrhea: 4 to 6 stools per day over Baseline; IV fluids indicated (<24 hours; not interfering with ADL) Colitis: abdominal pain; blood in stool	Withhold avelumab therapy Symptomatic treatment	If improves to Grade ≤ 1 : Resume avelumab therapy If persists >5-7 days or recurs: Treat as Grade 3 or 4
Grade 3 to 4 Diarrhea (Grade 3): ≥ 7 stools per day over Baseline; incontinence; IV fluids ≥ 24 h; interfering with ADL Colitis (Grade 3): severe abdominal pain, medical intervention indicated, peritoneal signs Grade 4: life-threatening, perforation	Withhold avelumab for Grade 3 Permanently discontinue avelumab for Grade 4 or recurrent Grade 3 1.0 to 2.0 mg/kg/day prednisone IV or equivalent Add prophylactic antibiotics for opportunistic infections Consider lower endoscopy	If improves: Continue steroids until Grade ≤ 1 , then taper over at least 1 month; resume avelumab therapy following steroids taper (for initial Grade 3) If worsens, persists >3 to 5 days, or recurs after improvement: Add infliximab 5 mg/kg (if no contraindication). Note: infliximab should not be used in cases of perforation or sepsis

Dermatological irAEs		
Grade of Rash (NCI-CTCAE v4)	Initial Management	Follow-up Management
Grade 1 to 2 Covering \leq 30% body surface area	Continue avelumab therapy Symptomatic therapy (for example, antihistamines, topical steroids)	If Grade 2 persists $>$ 1 to 2 weeks or recurs: Withhold avelumab therapy Consider skin biopsy Consider 0.5-1.0 mg/kg/day prednisone or equivalent. Once improving, taper steroids over at least 1 month, consider prophylactic antibiotics for opportunistic infections, and resume avelumab therapy following steroids taper. If worsens: Treat as Grade 3 to 4

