Grade 2 AST or ALT >3.0 to ≤ 5 x ULN and/or total bilirubin >1.5 to ≤ 3 x ULN	Withhold avelumab therapy Increase frequency of monitoring to every 3 days	If returns to Grade ≤ 1 : Resume routine monitoring; resume avelumab therapy If elevation persists >5 to 7 days or worsens: Treat as Grade 3 to 4
Grade 3 to 4 AST or ALT >5 x ULN and/or total bilirubin >3 x ULN	Permanently discontinue avelumab therapy Increase frequency of monitoring to every 1 to 2 days 1.0 to 2.0 mg/kg/day prednisone or equivalent Add prophylactic antibiotics for opportunistic infections Consult gastroenterologist/hepatologist Consider obtaining MRI/CT scan of liver and liver biopsy if clinically warranted	If returns to Grade ≤ 1 : Taper steroids over at least 1 month If does not improve in >3 to 5 days, worsens or rebounds: Add mycophenolate mofetil 1 gram (g) twice daily If no response within an additional 3 to 5 days, consider other immunosuppressants per local guidelines

Renal irAEs		
Grade of Creatinine Increased (NCI-CTCAE v4)	Initial Management	Follow-up Management
Grade 1 Creatinine increased > ULN to 1.5 x ULN	Continue avelumab therapy	Continue renal function monitoring If worsens: Treat as Grade 2 to 3 or 4
Grade 2 to 3 Creatinine increased >1.5 and ≤6 x ULN	Withhold avelumab therapy Increase frequency of monitoring to every 3 days 1.0 to 2.0 mg/kg/day prednisone or equivalent Add prophylactic antibiotics for opportunistic infections Consider renal biopsy	If returns to Grade ≤1: Taper steroids over at least 1 month, and resume avelumab therapy following steroids taper If worsens: Treat as Grade 4
Grade 4 Creatinine increased >6 x ULN	Permanently discontinue avelumab therapy Monitor creatinine daily 1.0 to 2.0 mg/kg/day prednisone or equivalent Add prophylactic antibiotics for opportunistic infections Consider renal biopsy Nephrology consult	If returns to Grade ≤1: Taper steroids over at least 1 month
Cardiac irAEs		
Myocarditis	Initial Management	Follow-up Management

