9. APPENDICES

Appendix 1. Immune-Related Adverse Events

The MedDRA PTs and clusters for irAEs are defined in the Safety Review Plan (SRP) for avelumab.

Immune-related AEs (irAEs) will be programmatically identified as outlined in Table 16. This case definition is hierarchical, ie, each step is only checked for patients and events that have already met the prior step.

Table 16. Case Definition for irAEs

Step	Selection Criteria	Additional Notes
1	Event selected based on a list of pre-specified MedDRA PTs within clusters. These are included in the SRP as Tier1 events (Immune-mediated xxxx). If AE matches the list then it is in for the next step	
2	AE onset during 1 st study drug administration or anytime thereafter through 90 days after last dose of study treatment.	This is regardless of start of new anti-cancer drug therapy and regardless of TEAE classifications
3	Answer in the AE eCRF page to ‘Was another treatment given because of the occurrence of the event’ is ‘YES’	
4	AE treated with corticosteroids or other immunosuppressant therapy. For endocrinopathies only: AE required hormone replacement	Look in the conmed pages for AE identifiers that match the AEs from Step 3. For each of such AEs if A) OR B) below are met then the AE is in for the next step A) conmed ATC code is in (H02A, H02B, H02C, D07, A01AC, S01BA, S01BB, L04AA, L04AB, L04AC, L04AD, L04AX) and AE PT is in any of the irAE clusters. B) conmed ATC code is in (H03A, H03B) and AE PT is in one of the irAE clusters associated with “Immune-mediated endocrinopathies”

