
5
	
A) No clear etiology (other than immune mediated etiology)
 
B) Histopathology / biopsy consistent with immune-mediated event
 
Event is in if [Answer to 5B1 and 5B2 is YES (regardless of answer to 5A)] OR [Answer to 5B1 is YES AND answer to 5B2 is NO AND answer to 5A is NO] OR [Answer to 5B1 is NO AND answer to 5A is NO]
	
A) From the AE eCRF page Is the AE clearly related to an etiology other than immune-mediated etiology? Yes / No If answer is Yes, check all that apply:
 
 • Underlying malignancy / progressive disease. • Other medical conditions. • Prior or concomitant medications / procedures. • Other. Specify. 
B) From the AE eCRF page B1) Was there a pathology /histology evaluation performed to investigate the AE? Y/N B2) If answer to the above is Yes, does the pathology/histology evaluation confirms an immune mediated mechanism for the AE? Y/N B3) If pathology / histology evaluation performed to investigate the AE, provide summary of relevant findings of the pathology /histology report. (Free Text)

----------	---	--

The data set associated with irAEs may be refined based on medical review. The final data set including any changes based on medical review (eg, addition of cases that are not selected by the programmatic algorithm) will be the basis of the irAE analyses.

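### The SAP's irAE algorithm requires steroid, immunosuppressant or hormone treatment before it reads etiology or histology, so some low-grade irAEs managed by withholding avelumab reach the irAE tables only through optional medical review

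*SAP*

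**What the plan says.** SAP 3.5.1 names irAEs and infusion-related reactions as the events of special interest and states: "The criteria for classification of an AE as an irAE or IRR are described in Appendices 1 and 2, respectively". Appendix 1, Table 16 then sets five steps for an irAE:

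1. The preferred term is on a pre-specified list.
2. Onset falls between the first study drug administration and 90 days after the last dose, whatever the TEAE status.
3. The eCRF question "Was another treatment given because of the occurrence of the event" is answered yes.
4. "AE treated with corticosteroids or other immunosuppressant therapy", identified by ATC code. For endocrinopathies, codes H03A and H03B also count.
5. Either there is no clear other etiology, or there is "Histopathology / biopsy consistent with immune-mediated event".

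The steps are strictly ordered: "This case definition is hierarchical, ie, each step is only checked for patients and events that have already met the prior step". A note after the table allows medical review to change the resulting data set, gives the addition of unselected cases as an example, and makes the reviewed data set the basis of the irAE analyses.

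Protocol Appendix 9 gives the initial management of Grade 2 diarrhea/colitis as "Withhold avelumab therapy Symptomatic treatment" and of Grade 2 hepatic irAEs as "Withhold avelumab therapy Increase frequency of monitoring to every 3 days". Protocol 7.1.2.1 treats any suspected potential irAE as an event of special interest, with no treatment condition.

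**The concern.** A definition that asks how an event was treated before it asks what the event was will miss irAEs that were managed without the listed drugs. The protocol directs exactly that, at first, for two Grade 2 categories. An event that costs the patient avelumab doses and then resolves can be a true irAE and still not be selected.

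What is at stake is the description of low-grade immune toxicity. irAEs are Tier-1 events in SAP 6.6.4, with counts, risk differences and two-sided p-values for experimental against comparator arm. If the algorithm's output is taken largely as it stands, the overall irAE counts in the avelumab arms may be too low, and a reader of the tables would have no way to tell by how much.

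**Working it through.** The plan states no figure that depends on this definition, so the check is a trace of the protocol's management rows through Table 16.

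| Protocol Appendix 9 row, managed as written and resolving | Step 3 (other treatment given) | Step 4 (qualifying drug) | Selected? |
|---|---|---|---|
| Grade 2 hepatic: hold, monitor more often | No | Not reached | No |
| Grade 2 diarrhea/colitis: hold, symptomatic treatment | Yes, if a drug is given | No | No |
| Grade 1 pneumonitis: holding optional, monitor | No | Not reached | No |
| Grade 1 diarrhea/colitis, hepatic, creatinine: avelumab continues | At most symptomatic treatment | No | No |
| Grade 1 to 2 rash: symptomatic, such as antihistamine or topical steroid | Yes | Only if a steroid is used (D07 and H02 are listed) | Depends |
| Grade 2 pneumonitis; Grade 2 to 4 renal; Grade 3 to 4 GI, skin, lung and liver; immune-mediated myocarditis; other confirmed Grade 2 to 4 irAEs | Yes | Yes, prednisone is listed | Goes on to Step 5 |

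**Escalation limits the gap.** Grade 2 GI events that persist beyond 5 to 7 days or recur, and Grade 2 hepatic events that persist beyond 5 to 7 days or worsen, move to the Grade 3 to 4 rows, which list prednisone. The gap is confined to events that settle before that.

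**It does not depend on Amendment 2.** Table 6, in force until then, also delayed avelumab for Grade 2 diarrhea/colitis and Grade 2 liver test elevation, and brought in steroids only on persistence, recurrence or worsening. Amendment 2 says the final analysis was already complete, so Table 6 is the guidance relevant to the analysed data.

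**Order of Steps 4 and 5.** Step 5 accepts an event with confirming histology (5B1 and 5B2 both yes) whatever the answer on other etiologies. The table thus treats histology as decisive, yet never reads it for an event that failed Step 3 or 4.

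**Where an unselected event still appears.** If treatment-emergent, it stays in the TEAE tables by preferred term and grade (SAP 6.6.1.1) and, where avelumab was held and this was recorded as an interruption, in the interruption tables (6.6.1.3). Hepatic events can also appear in the liver test summaries (6.6.5.1). None of these marks it as an irAE, and 6.6.4 has no table of irAEs leading to interruption. Summarised safety data stop at 30 days after last dose, or earlier if a new anti-cancer drug starts (5.2.7). Step 2 runs to 90 days. An unselected event with onset after the on-treatment period is therefore listed but in no summary.

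**Size.** The only grade distribution is the Phase 1 data in protocol 1.2.2.2: of 69 potential irAE events, 26 were Grade 1 and 29 Grade 2, so (26 + 29)/69 = 55/69 = 79.7% were low grade. Let *u* be the unknown share of low-grade events that got no qualifying drug, and assume all higher-grade events got one. The share of events missed by the algorithm is then 0.797 × *u*, which runs from 0% (*u* = 0) to 79.7% (*u* = 1). That range is too wide to be an estimate. It shows only that most potential events were in the grades where the rule can bite.

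**The case against.** The strongest reply is that the algorithm's output is not the analysis set. Appendix 1 provides for medical review and names the addition of unselected cases, which is the very omission at issue. A reader might infer that untreated irAEs drop out of every irAE table; the documents do not support that. What stands is that the review is permitted rather than required, and the SAP gives it no criteria. Nor do the documents say that reviewers know the arm: an open-label design does not by itself establish it.

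Other tempting readings also go too far:

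- *Many irAEs are managed by withholding alone.* A firm hold with no drug listed is one row for an established irAE, Grade 2 hepatic. Grade 2 GI adds symptomatic treatment, and the Grade 1 pneumonitis hold is optional.
- *Discontinuations are understated.* The rows that stop avelumab permanently by grade or recurrence list steroids, so events managed as written normally pass Step 4.
- *Biopsy-proven events are lost in number.* Biopsy is mostly suggested in rows that also list or suggest steroids, and a suspected or confirmed immune cause of myocarditis moves to a row listing prednisone. The ordering flaw is real but should seldom matter.
- *The SAP contradicts the protocol.* Protocol 7.1.2.1 serves management and reporting, and protocol 9.5 leaves risk comparisons to the SAP. A narrower analysis definition is a legitimate choice.

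The Phase 1 figures are also weak support for size. They pool tumor types and study parts, and 23 of the 69 events were judged unrelated to treatment. In the 75-patient ovarian cohort (protocol 1.2.2.4) the immune-related events were hypothyroidism (5), arthritis (2) and myositis (1), with none hepatic or GI; hypothyroidism has its own hormone route in Step 4. Finally, SAP 3.5.1 calls safety analyses generally exploratory, and 6.6.4 limits these p-values to screening.

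These points narrow the concern to low-grade events. They do not remove it.

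**Conclusion.** The point holds in a limited form. Table 16 does not select irAEs managed without a qualifying drug, chiefly Grade 2 hepatic and Grade 2 diarrhea/colitis events that resolve after avelumab is withheld. Their place in the irAE tables then rests on an optional review without stated criteria. Low-grade and overall irAE incidence may be understated; Grade 3 or higher and discontinuation tables should be little affected.

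The size is unknown, since no document gives the share of irAEs without a qualifying treatment, and any particular drop in incidence would be a guess. The conclusion assumes that sites followed the protocol's guidance and that the affected preferred terms are on the Step 1 list, which sits in the Safety Review Plan and is not among these documents. The remedy is cheap and affects what can be concluded about irAE incidence, so it should be made.

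**What to change.** In SAP Appendix 1:

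1. Beside the current irAE tables, add one summary by arm, cluster and grade of events meeting Steps 1, 2 and 5 regardless of treatment given, showing how many led to a study drug being interrupted or withdrawn. Step 2's 90-day window would also bring in events that the TEAE summaries leave out.
2. Let an event that meets Steps 1 and 2 and has confirming histology (5B1 = Yes and 5B2 = Yes) qualify without Steps 3 and 4.

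The cost is SAP wording and one table. Table 16 takes the Step 5 answers from the AE eCRF page and states no treatment condition for asking them, so no new data should be needed; confirm that the form asks them for untreated events too. The downside is lower specificity: rash and diarrhea also occur with PLD (protocol 5.2.6), so the broader table will admit some events that are not immune-mediated. It should therefore supplement the current definition, not replace it. No clinical rule changes.
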